The treatment sample will be 144 subjects with PTSD as a consequence of any trauma (e.g., motor vehicle and accidents, burns and other injuries, combat, World Trade Center attack, etc.) ($n=114$), as well as telemedicine subjects with PTSD who live in Vermont, New York State, New Jersey, Connecticut, and Pennsylvania ($n=30$). Subjects will be randomly assigned to one of two treatment groups: imaginal exposure (IE) plus DCS ($n=72$) or IE plus placebo ($n=72$). Both experimental treatment groups will complete a standardized exposure therapy protocol similar to the IRB-approved protocol of the PI's current DCS VR exposure therapy study. The therapy is 12-14 weekly sessions that include well-validated and widely used cognitive-behavioral treatment (CBT) interventions: imaginal exposure, graduated in vivo exposure, psycho-education, relaxation training, engaging in pleasurable events, and cognitive reframing. Subjects will be instructed to take the pill they are provided (i.e., DCS or placebo) 90

minutes prior to all sessions that include exposure (sessions 3 on) and compliance will be assessed weekly. To assess emotional engagement and habituation during imaginal exposure, in 5-minute intervals, the subject rates his/her Subjective Units of Distress (SUDS) level, with 0 indicating no distress and 100 indicating the maximum. (Treatment is described under Section A.7 and a treatment manual is attached in Appendix A.) During treatment, subjects will be assessed by an independent evaluator after sessions 3, 6, and 10, to determine at what point, if any, differences between groups begin to emerge. Subjects will complete a limited battery of self-report questionnaires on a weekly basis prior to the treatment session and will be assessed for potential side effects at each session in which medication is taken.

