 Sample size estimates were based on the formula outlined by Diggle et al.⁴⁶ for longitudinal studies. Although our pilot data and the published DCS phobia treatment studies suggest large effect sizes for a combined DCS treatment, we followed the recommendations by Kraemer et al.⁴⁷ who suggested that the critical effect size at which the power is computed to be 80% should be the threshold below which clinicians are unlikely to be interested in the effect. Adopting the procedures used in a large-scale study of Vietnam Veterans with PTSD⁴⁸, we designated a decline of 10 points on the CAPS (based on ½ a standard deviation) as the minimum clinically meaningful effect, which corresponds to a conservative (small-moderate) estimated effect size of $d = .5$. The calculations were based on the assumption of a strong correlation within subjects over time, $\rho = .6$, and also assume $\alpha = .05$. The number of assessments for the primary outcome measure (CAPS scores) was 5 (baseline, 3 clinical assessments during treatment, and post). A sample size of 34 per group was found to be sufficient at 80% power to detect the effect. Estimating an attrition rate of 30%, we plan to enroll 114 (57 per group) to ensure that an adequate sample remains by post-treatment and follow up. In addition, pilot subject data ($n=10$) will be collected to investigate the feasibility and acceptability of telemedicine to provide imaginal exposure (IE) therapy for PTSD.

Literature Cited:

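### The 34 per group appears to count pre-treatment CAPS as an outcome visit carrying the full effect; name a baseline-adjusted primary contrast and recompute

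*Combined protocol and SAP*

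**What the plan says.** The paragraph headed Statistical considerations is the only place where the plan says how CAPS data enter the design. "Sample size estimates were based on the formula outlined by Diggle et al", a longitudinal-data textbook, but the variant (average difference, slope or other) is not named. On the effect: "we designated a decline of 10 points on the CAPS (based on ½ a standard deviation) as the minimum clinically meaningful effect", given as d = .5. One within-subject correlation, .6, and alpha .05 are assumed; the sidedness of alpha is not given. Then: "The number of assessments for the primary outcome measure (CAPS scores) was 5 (baseline, 3 clinical assessments during treatment, and post". The result: "A sample size of 34 per group was found to be sufficient at 80% power to detect the effect". On enrolment: "Estimating an attrition rate of 30%, we plan to enroll 114 (57 per group".

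Research Design and Methods places the capsule "minutes prior to all sessions that include exposure (sessions 3 on", and the on-treatment assessments after sessions 3, 6 and 10. Baseline CAPS therefore precedes all study medication. The same section randomises 72 per arm once the 30 telemedicine subjects are included.

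The documents state no primary analysis model, and they do not mention a baseline covariate, a change score or a constraint on baseline means.

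**The concern.** Randomised arms can differ at baseline only by chance. If baseline is averaged in with the later visits, one fifth of the contrast has an expected difference of zero, and both the estimate and the power shrink. If the sample-size formula treats all five visits alike, it assumes a 10-point effect at a visit where none is possible, and the 80% is not the power of that contrast.

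The same measurement used as a covariate works the other way. With a correlation of .6 it removes a large part of the between-subject variance. The plan collects baseline CAPS but does not commit to using it like this. The choice among raw, change and adjusted analyses is left open, and their power differs materially.

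**Working it through.** **Inputs** (Statistical considerations): d = 0.5, so 10 points implies SD 20; rho = .6, taken as equal between all pairs of visits because one value is given; m = 5; alpha .05; power 80%. The squared sum (z_alpha + z_power)² is 6.183 one-sided and 7.849 two-sided. Variances below are in SD². Paired results are one-sided / two-sided.

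**1. Reproducing the 34.** For a time-averaged difference, n per group = 2(z_alpha + z_power)² V / d², with V = [1 + (m − 1)rho]/m.
- m = 5: V = (1 + 2.4)/5 = 0.68. One-sided, 2 × 6.183 × 0.68 / 0.25 = 33.6, so 34. Two-sided, 42.7, so 43.
- m = 4: V = (1 + 1.8)/4 = 0.70, giving 34.6 (35) / 44.0 (44).

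The match at m = 5 is exact, but it needs a one-sided alpha that the plan does not state. Dropping baseline without adjusting for it moves n only from 34 to 35.

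**2. Rival readings.**
- Slope, with 0.5 SD reached at the last of five equally spaced visits: n = 2(z_alpha + z_power)²(1 − rho)/[S × slope²], where S = 10 is the sum of squared deviations of visit times 0 to 4 and slope = 0.5/4 = 0.125. One-sided, 2 × 6.183 × 0.4/(10 × 0.015625) = 31.7, so 32. With assumed times 0, 3, 6, 10, 12 it is 30.
- Mean of the four later visits minus baseline: V = 0.70 + 1 − 1.20 = 0.50. Two-sided, 2 × 7.849 × 0.50/0.25 = 31.4 by the normal approximation, and 33 by t-test.

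Both come close and neither gives 34.

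**3. The unadjusted five-visit average, if used.** Assume zero effect at baseline and 0.5 SD at each later visit. The mean difference is 4 × 0.5/5 = 0.4 SD, or 8 points. The required n is 2 × 6.183 × 0.68/0.16 = 52.6 (53) one-sided and 66.7 (67) two-sided. Power = Φ(0.4/√(2 × 0.68/n) − z_alpha):

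| n per arm | One-sided | Two-sided |
|---|---|---|
| 34 (stated requirement) | 64% | 52% |
| 40 (57 × 0.7 = 39.9) | 70% | 58% |
| 50 (72 × 0.7 = 50.4) | 78% | 68% |
| 57 (enrolled, no loss) | 83% | 74% |
| 72 (randomised, no loss) | 90% | 83% |

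**4. With baseline as covariate.** Adjustment subtracts rho² = 0.36 from the variance. Power at 34 per arm:

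| Contrast | Variance | One-sided | Two-sided |
|---|---|---|---|
| Mean of four later visits, adjusted | 0.70 − 0.36 = 0.34 | 97% | 94% |
| Post visit, adjusted | 1 − 0.36 = 0.64 | 82% | 73% |
| Post visit, unadjusted | 1.00 | 66% | 54% |

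For 80% power the adjusted four-visit mean needs 17 / 22 per arm, and the adjusted post visit 32 / 41.

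**5. Sensitivity.** Keep .6 among the later visits but let baseline correlate only .4 with them (my assumption). The adjusted four-visit variance is 0.70 − 0.16 = 0.54, and power at 34 is 88% / 80%. At .3 it is 84% / 75%.

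Now keep rho = .6 but let the effect build in proportion to capsules taken: 1, 4, 8 and 9 of nine, ignoring the optional extra sessions (also my assumption). The adjusted four-visit mean then has 70% / 58%, while the adjusted post visit keeps 82% / 73%.

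**The case against.** The strongest reply is that this paragraph only sizes the trial. It lists when CAPS is measured and names no model, estimand or contrast, so an unadjusted five-visit average is inferred. Other wording points towards change over time: the Summary asks about faster as well as larger improvement, Research Design and Methods places the mid-treatment assessments to find when the arms separate, and the effect is expressed as a decline. In a slope or arm-by-visit analysis baseline belongs among the responses and dilutes nothing. The formulas for those readings come within a few patients of 34, and the exact match needs an unstated one-sided alpha.

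Most of this stands. It lowers confidence in the reading, but it does not supply the missing statement: no slope, change or adjusted analysis is written down either.

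A reader might go further than the documents allow in three ways:
- **That the trial's estimate is biased towards no effect.** That holds only for an average the plan never says it will use.
- **That the trial is too small.** Under baseline adjustment 34 per arm is ample for the four-visit mean. Enrolment is 57, or 72 with telemedicine, and even the diluted average reaches 90% / 83% at 72 before losses.
- **That listing baseline as a response is itself an error.** It is legitimate when the arm means are constrained equal there.

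**Conclusion.** The point holds in a limited form, with moderate confidence. The plan counts a pre-capsule visit among its outcome assessments. Its sample size is matched exactly, among the formulas tried, only by one that gives that visit the full effect, and nothing commits the analysis to baseline adjustment.

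The harm depends on the analysis eventually chosen. An unadjusted five-visit average would report 8 points for a true 10 and miss 80% power at the plan's own evaluable target. An adjusted analysis of the four-visit mean halves the variance from 0.68 to 0.34 SD² and more than recovers the loss.

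These sizes rest on SD 20, equal correlation .6 between all visits, and the full effect at each of the four later visits. A weaker correlation with baseline reduces the gain. An effect that builds up makes the post-treatment contrast the less sensitive choice. The missing sidedness of alpha is a separate gap, but it changes every figure here.

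**What to change.** Specify one repeated-measures model for post-baseline CAPS with arm, visit, arm-by-visit and baseline CAPS as covariate. Equivalently, keep baseline as a response with arm means constrained equal at that visit. Name one primary contrast from that model: the arm difference at post-treatment, or the mean over the assessments after sessions 3, 6 and 10 and at post. The six-month visit may enter the same model but should not be counted in the primary contrast unless that is stated.

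Then rewrite Statistical considerations for that contrast. Give the formula variant, the visits it covers, the correlation assumed between baseline and later visits (with a lower value as sensitivity), the sidedness of alpha, and the power at the number expected to remain after attrition.

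The cost is wording and a recalculation. Baseline CAPS is already collected, and no patients or visits are added.
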